Official Title: Medication Enhanced CM for Cocaine Dependence

NCA Number: 02111798

Document Date: January 2, 2019

Date: January 2, 2019

Principal Investigator: [name].

Application Number: NA00090062

JHM IRB - eForm A - Protocol

• Use the section headings to write the JHM IRB eForm A, inserting the appropriate material in each. If a section is not applicable, leave heading in and insert N/A.

 When submitting JHM IRB eForm A (new or revised), enter the date submitted to the field at the top of JHM IRB eForm A.

1. Abstract

Provide no more than a one page research abstract briefly stating the problem, the research hypothesis, and the importance of the research.

The efficacy of behavior therapies may be enhanced by certain medications, particularly those that act on dopaminergic systems. This project will examine effects of bupropion on initiation and maintenance of cocaine abstinence in a population of cocaine dependent methadone maintenance patients. Bupropion appears to be the most promising medication for this purpose because of its previously demonstrated efficacy and safety as well as its pharmacological actions at dopamine systems.

Methadone maintained cocaine dependent study participants (N = 100) will be stratified according to whether or not they stop their cocaine use during initial exposure to an abstinence incentive (contingency management) procedure and will be randomly assigned to receive bupropion XL (300mg/day) versus placebo for the remainder of the study. Our hypothesis is that bupropion as compared to placebo treatment will both enhance rates of abstinence initiation in those who have difficulty stopping cocaine and retard rates of relapse in those who initially stopped their cocaine use.

Participants will receive a CM schedule that is tailored to their initial CM response and outcomes will be tracked over a 6-month time frame that includes assessment of drug use outcomes after incentives have stopped. In addition, the project will provide novel information about mechanisms of medication effects by measuring subjective drug effects, drug vs money choices, and self-reports of pleasure derived from daily non-drug activities. We hypothesize that bupropion compared to placebo participants will report non-drug activities as more pleasurable (reinforcing), will engage in more of them and that measures of non-drug reinforcement will mediate abstinence outcomes.

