Overall, this research will provide new and valuable information about combined behavioral-pharmacological treatments and specifically the conditions under which medication may enhance effects of CM. If hypothesized synergies can be demonstrated, the study will point the way to a significant advance in improved treatment outcomes for this critical group of drug abusers. The proposed study is compelling because it conceptually differentiates the two key clinical issues in treatment of stimulant abusers- abstinence initiation and relapse prevention. It uses a design that efficiently and effectively tests a combined treatment approach for each clinical issue and as well examines cognitive function and reinforcement-based mediators. The research will add to understanding of the interplay between brain reinforcement systems and drug-seeking behavior. Finally, it will make an important contribution to behavioral therapy development by exploring a novel solution to limitations previously noted for CM that include lack of response in some patients and relapse after withdrawal of incentives.

2. Objectives (include all primary and secondary objectives)

Specific aims of the project are the following:

- a. Examine in those who initially achieve abstinence with CM the effects of bupropion XL (300 mg/day) versus placebo on 24-week abstinence outcomes during and after CM. Hypothesis: Among participants who achieve initial abstinence, those treated with bupropion compared to placebo will have significantly longer delays to resumption of drug use and higher rates of abstinence at 24-weeks.
- b. Examine in those who initially fail to achieve abstinence with CM the effects of active bupropion XL (300 mg/day) versus placebo medication on subsequent abstinence initiation outcomes. Hypothesis: Among participants who failed to achieve initial abstinence, those treated with bupropion vs placebo will have significantly higher rates of abstinence at 12 and 24 weeks.
- c. Identify mechanisms of bupropion-enhanced outcomes by administering self-report instruments that assess response to non-drug reinforcement.

 Hypothesis1: Bupropion compared to placebo participants will report both money and non-drug activities as more reinforcing and will engage in more of the latter.
 - Hypothesis 2: Enhanced non-drug reinforcement will mediate abstinence outcomes

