well as any necessary covariates, including cocaine positive vs negative urine tests prior to random assignment as a covariate. Generalized linear mixed models (GLMM) will be used to analyze repeated measures data, since this technique can include participants with incomplete data without resorting to imputation. This approach has been found to minimize bias and maximize power in cases of incomplete follow-up (see Hedden et al, 2009). Data will then be examined using the nonbinary method described by McCann and Li (2012) in which participants who meet an end of study threshold of success (1 week EOS abstinence) are assigned values indicating their number of beyond threshold weeks of success (in our case 1-24). This distribution will be analyzed as a function of drug condition using a two-sided Vander Waerden two-sample test (Permutt and Berger, 2000).

All other analyses will be conducted in the overarching group that includes those abstinent and actively using at baseline. This approach will allow us to preserve all study Aims with a reduced sample size that will ensure the study can be completed in the time allowed.

The data analysis plan consists of the following:

- 1) Comparison of groups for baseline differences. Participants will be compared as a function of medication group on baseline characteristics to determine whether they are comparable with respect to general demographic features, baseline drug use, and reinforcement measures (drug vs. money relative reinforcing potency scale, Snaith-Hamilton Pleasure scale). Groups will be compared using t tests for continuous measures and chi-square tests for categorical characteristics. If medication groups are found to differ on baseline measures, then these characteristics will be used as covariates in subsequent analyses assessing treatment effect.
 - 2) Primary outcome analyses: (see above)
- 3) Secondary outcome analyses: The main secondary outcome measure will be biochemically-confirmed abstinence from opiates. We hypothesize that participants receiving bupropion will have a higher proportion of opiate abstinent samples as well as for cocaine. Analyses conducted to assess the treatment effect for opiate use will be identical to those used for cocaine use (described above).

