- 4) Other Secondary Outcome Analyses: Other secondary outcomes are reinforcement measures, such as the drug vs. money relative reinforcing potency scale, the Snaith-Hamilton Pleasure scale, as well as time engaging in non-drug-related activities and changes in neurocognitive performance. These measures will be collected at baseline and throughout the study. Analyses will be the same as those described for cocaine (GEE with medication group X time as factors). Participants receiving bupropion are hypothesized to find non-drug activities to be more reinforcing than participants receiving placebo, and to engage in more of them.
- 5) Exploratory mediation analysis. Measures collected at baseline including demographic characteristics, intake drug use severity, non-drug reinforcement, non-drug activities and neurocognitive performance will be examined separately to determine whether any predicts outcome independently of treatment. Next, we will add each of these measures to the models that assessed treatment effect, used for primary outcome analyses. If the treatment effect becomes diminished by addition of a third variable, this will be considered preliminary evidence that the third variable may mediate the effect of the treatment.

7. Risks

- a. Medical risks, listing all procedures, their major and minor risks and expected frequency.
- b. Steps taken to minimize the risks.
- c. Plan for reporting unanticipated problems or study deviations.
- d. Legal risks such as the risks that would be associated with breach of confidentiality.
- e. Financial risks to the participants.

Bupropion XL is an FDA-approved antidepressant and smoking cessation pharmacotherapy and will be used in accordance with the prescription labeling instructions during this study. The extended release (XL) preparation allows for once-daily dosing and thus improved adherence. The medication will be titrated to an oral dose of 300 mg after 3 days at 150 mg daily. With a half-life of 21 hours, steady state is

reached after 8 days. Methadone maintenance is a long-standing and effective usual care treatment for opioid dependence but does not directly impact the concurrent use of stimulants alcohol or other drugs.

Risks associated with Bupropion XL side-effects

Major risks of bupropion are summarized below; a complete list of potential side-effects is included in the consent form.

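### The only mediation analysis (Section 6, item 5) uses baseline measures, which treatment cannot change, so it cannot test Aim c Hypothesis 2

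*Combined protocol and SAP*

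**What the plan says.** The hypothesis appears twice. Section 1 (Abstract) expects that "measures of non-drug reinforcement will mediate abstinence outcomes". Section 2 (Objectives), aim c, has "Hypothesis 2: Enhanced non-drug reinforcement will mediate abstinence outcomes". Section 4, in the incentive schedule for initially drug-negative participants, gives the mechanism: bupropion should delay relapse because it makes non-drug reinforcers more salient.

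Section 6, item 5 is headed as an exploratory mediation analysis. Its inputs are "Measures collected at baseline including demographic characteristics, intake drug use severity, non-drug reinforcement, non-drug activities and neurocognitive performance". It has two steps:

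- Each measure is examined for whether it predicts outcome independently of treatment.
- "Next, we will add each of these measures to the models that assessed treatment effect", meaning the primary outcome models.

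The decision rule follows: "If the treatment effect becomes diminished by addition of a third variable, this will be considered preliminary evidence that the third variable may mediate". No size of reduction, test or interval is given.

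Section 6, item 4 covers the reinforcement scales, non-drug activities and neurocognitive performance as secondary outcomes. It says "These measures will be collected at baseline and throughout the study", and "Analyses will be the same as those described for cocaine (GEE with medication group X time as factors".

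**The concern.** A mediator is a variable that treatment changes and that in turn changes the outcome. Item 5 offers only values fixed before randomisation, so the first link is missing by design. Item 4 asks whether bupropion changes the reinforcement measures, which is Hypothesis 1. No item links the on-treatment values of those measures to abstinence, so Hypothesis 2 has no analysis that can address it.

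The practical risk is a misleading report. Under the stated rule, a baseline characteristic that happens to shrink the treatment coefficient could be described as a possible mediator. A true mediator, represented only by its baseline value, could be passed over.

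**Working it through.** **1. Timing.** Section 4 gives the sequence.

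- CM Lead-In: the baseline assessment is completed before the 6-week lead-in.
- Medication: everyone starts on placebo capsules in week 1, and randomisation comes in week 3 at the earliest.
- Stratification and Random Assignment: those who clearly will not qualify as responders are randomised at the start of week 6.
- Study Measures: the reinforcement and activity instruments are repeated at weeks 6, 12, 18, 24 and 30.

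Every value that item 5 enters therefore predates active drug.

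**2. Consequence.** Write T for treatment, B for the baseline value of a measure, M for its on-treatment value, a for the effect of treatment on the candidate mediator and b for the effect of the candidate on outcome. On the linear-predictor scale the indirect effect is a × b. For B, randomisation gives E[B | T=1] = E[B | T=0], so a = 0 and a × b = 0 whatever b is. This needs no numbers.

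**3. What can move the coefficient.** Adding B can shift the treatment coefficient through chance imbalance, loss of participants with missing covariate values, or, in a logistic model without a person random intercept, non-collapsibility. Non-collapsibility tends to increase the coefficient, the opposite of what the rule looks for.

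**4. Illustration, one outcome per person.** The documents give no effect sizes, so all are assumed. M = ρB + √(1−ρ²)·e + aT; logit P(Y=1) = −0.5 + cT + bM; b = 1; 50 per arm; 4,000 runs. Full mediation is a = 0.8, c = 0. No mediation is a = 0, c = 0.8. The first three result columns are mean treatment log-odds ratios. Smaller means a smaller absolute coefficient. The last two columns are the share of all runs with a positive unadjusted effect that fell by more than 10%.

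| Truth | ρ | No covariate | + B | + M | Smaller with B | >10% drop, B | >10% drop, M |
|---|---|---|---|---|---|---|---|
| Full mediation | 0.3 | 0.684 | 0.704 | −0.001 | 41.1% | 8.1% | 95.0% |
| Full mediation | 0.6 | 0.676 | 0.728 | −0.016 | 34.4% | 12.9% | 94.6% |
| No mediation | 0.3 | 0.682 | 0.700 | 0.834 | 41.2% | 9.3% | 12.5% |
| No mediation | 0.6 | 0.692 | 0.743 | 0.850 | 34.5% | 13.4% | 12.4% |

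The two B columns are nearly the same whether mediation is complete or absent. The M column separates the two cases.

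**5. Illustration, closer to the primary model.** Section 6 says "Generalized linear mixed models (GLMM) will be used to analyze repeated measures data", although item 4 describes the cocaine analysis as GEE. This illustration takes the mixed-model reading. M = ρB + aT + √(1−ρ²)·e; logit P = −0.6 + 1.5(U−0.5) − 0.5·time + bM + u, where U is pre-randomisation urine status and u is a person random intercept with SD 1.5 or 2.5. There are 18 weekly outcomes, full mediation, and six sets (a, b, ρ) with a from 0.5 to 1.0, b of 0.8 or 1.2, and ρ from 0.3 to 0.8. The fitted model has medication, time, their interaction and U.

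- 4,000 per arm (SD 1.5): the treatment log-odds ratio is 0.39 to 1.19 across sets, 0.39 to 1.18 with B added, and −0.03 to 0.01 with M added.
- 50 per arm, among trials with a positive unadjusted estimate: the effect is smaller in 48–54% of trials with B, in 49–51% with a pure-noise covariate (SD 1.5), and in 99–100% with M.

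**6. Several candidates.** If each of five irrelevant covariates has an even chance of shrinking the coefficient, at least one does so with probability 1 − 0.5^5 = 97%. The simulation gave 97–98%. The median change is only 1–4%.

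**The case against.** *Item 5 may name instruments, not visits.* Three of its five domains are item 4's repeated measures. But demographics and intake severity have no on-treatment version, the first step is a predictor analysis, and no later visit is named. Even on this reading, the plan must say which visit's value enters.

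*The first step could act as a screen.* With an assumed 5% screen, five noise covariates would give 1 − (1 − 0.05 × 0.5)^5 = 12%, not 97%. That is fair, and the 97% applies only without a screen. No screen is stated, however, and a screen would still pass any prognostic baseline variable, none of which can be a mediator.

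*A 1–4% change would not be reported as a diminished effect.* This stands as a limit on the any-decrease percentages. A 10% threshold does not rescue the rule, though: the table shows 8.1–12.9% with baseline values under full mediation and 9.3–13.4% under none.

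*Item 1 already adjusts for baseline differences between groups.* It adjusts only for differences it detects, and adjustment does not turn a baseline value into a mediator.

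*Part of item 5 is legitimate.* This stands. Aim d asks whether pre-treatment measures predict response to incentives, and the first step is close to that. If Section 3's mention of patient-level mediators is meant loosely, item 5 is a predictor or moderator analysis under the wrong label, and Hypothesis 2 still lacks an analysis.

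*The analysis is exploratory and worded cautiously.* This also stands, and it keeps the severity low.

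**Conclusion.** The concern holds: item 5 is wrong as written. The conclusion rests on the order of baseline, randomisation and drug in Section 4, not on the simulations. Their percentages depend on assumed effect sizes and on the model, and serve only to show that the rule responds alike to a true mediator's baseline value and to an unrelated variable. The consequence is an invalid mediation inference for one stated hypothesis. No data are lost, and the primary, main secondary and safety analyses are untouched. It should be fixed, at low severity.

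**What to change.** Reword item 5.

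- For Hypothesis 2, use post-randomisation values of the non-drug reinforcement and activity measures. Name a visit that is clearly after randomisation for everyone, for example week 12. Week 6 is unsuitable because non-responders are randomised at its start.
- Take abstinence after that visit as the outcome, for example weeks 13–24.
- Adjust for the measure's baseline value and the responder stratum.
- Report the indirect effect with a confidence interval, as exploratory, and state that mediator–outcome confounding limits it. Adjustment for abstinence before the mediator visit can be a sensitivity analysis.
- Relabel the baseline-variable models as predictor analyses, or as moderator analyses with a treatment interaction, and delete the diminished-effect rule for them.

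The cost is one rewritten paragraph and a little analysis time, since all the data are already scheduled. There are three downsides. First, precision is poor at 50 per arm: in the simulation limited to weeks 13–24, the indirect effect averaged 0.41 to 1.24 on the log-odds scale with an SD of 25–52% of its mean. A 95% interval is then about 1.96 × 25% = ±49% to 1.96 × 52% = ±102% of the estimate, even with the mediator measured without error. Second, outcomes up to the mediator visit drop out, and so do weeks after 24 if the example window is used. Third, early abstinence may raise week-12 activities and also predict later abstinence, so confounding remains possible.

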The aim of this study is to evaluate whether bupropion will enhance cocaine abstinence among methadone-maintained patients who are abusing cocaine. This is being evaluated in a double-blind context. Further, based on evidence that individuals with cocaine use disorder typically present to the clinic with a urine sample that is positive for cocaine (which predicts continued use) or negative for cocaine (which predicts abstinence), we had originally proposed to treat those individuals as two separate groups and run 2 parallel studies (presented as Primary Aims 1 and 2), using contingency management as a background platform to support either abstinence or relapse prevention, respectively. Each aim was intended to enroll 100 individuals (N=200) total, to enable equal distribution of bupropion (n=50) and placebo (n=50) within each aim.

Based on unanticipated difficulties with recruitment, we are now collapsing the two parallel studies into the same overarching study, such that Primary Aim 1 will now be examining the effects of bupropion XL vs. placebo on 24-week abstinence outcomes during and after exposure to a behavioral intervention (CM). We are reducing our sample size to 100 individuals, which still preserves the required 50 participants per medication group that was identified in our power analyses as necessary to detect an effect of the medication. This approach will allow us to achieve our primary aim of determining whether bupropion will enhance cocaine abstinence despite challenges with recruitment and will enable this study to still provide clinically important information to advance the treatment of cocaine use disorder.

We are modifying our statistical plan to accommodate this change in sample size. We will retain the original primary outcome measure (biochemically-confirmed abstinence from cocaine), which will be assessed across all participants (independent of abstinence group) in the same statistical model. The endpoint will be binary (abstinent yes or no), and the treatment effect will be assessed using a repeated-measures logistic regression model having two main effects: medication and time, plus their interaction, as

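### Item 5 takes any shrinkage of the treatment coefficient as preliminary evidence of mediation, without a test or interval, and applies this to baseline measures that medication cannot change

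*Combined protocol and SAP*

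**What the plan says.** Section 2, aim c, Hypothesis 2 is the mechanism hypothesis: "Enhanced non-drug reinforcement will mediate abstinence outcomes". The abstract repeats it, and the Background presents the design as suited to studying mediators.

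Section 6, item 5, labelled exploratory, is the only stated rule for judging mediation. It has three steps:

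- It starts from "Measures collected at baseline including demographic characteristics, intake drug use severity, non-drug reinforcement, non-drug activities and neurocognitive performance", which "will be examined separately to determine whether any predicts outcome independently of treatment".
- It continues: "Next, we will add each of these measures to the models that assessed treatment effect".
- It concludes: "If the treatment effect becomes diminished by addition of a third variable, this will be considered preliminary evidence that the third variable may mediate" the treatment's effect.

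The model in question is a "repeated-measures logistic regression model having two main effects: medication and time, plus their interaction", with covariates. Item 5 does not say whether the medication main effect or the interaction is the treatment effect to be watched.

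Item 4 separately analyses reinforcement, non-drug activity and neurocognitive measures over time by medication group: "Analyses will be the same as those described for cocaine (GEE with medication group X time as factors"). Item 5 does not refer to those results.

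**The concern.** The criterion compares two numbers: the treatment coefficient without the added variable and the coefficient with it. It is met whenever the second is smaller. With 50 per arm, an added variable that has nothing to do with mechanism still moves the coefficient a little, down almost as often as up.

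Timing makes this worse. A mediator lies on the path from treatment to outcome, so treatment must be able to change it. A measure taken before randomisation cannot be changed by treatment. Adding it can reveal chance imbalance or the usual effect of adjustment in a logistic model, but not mediation. Hypothesis 2 concerns reinforcement that is enhanced under treatment, which a baseline value cannot show.

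At stake is how aim c is read. A flagged variable would be offered as a lead on mechanism although the rule hardly separates mediators from other variables.

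**Working it through.** **Plan's own figure.** There is none to reproduce: the plan states no error rate or alpha for item 5.

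**Inputs from the plan.** 100 participants, 50 per medication group; five kinds of measure; a repeated-measures logistic model; any reduction counts.

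**Assumptions.** One variable per kind, none a mediator; the rule fires if the absolute treatment coefficient falls. Where the first step of item 5 is read as a gate, it is two-sided p<0.05. Variances, stratum effect, drug effect and prognostic strength are all assumed.

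**Formula.**

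- All five added, each an independent coin flip: 1 − 0.5^5 = 0.969.
- Same, with the five coefficient changes correlated at 0.3 or 0.5: 0.895 or 0.834.
- Gated, none prognostic: 1 − (1 − 0.05 × 0.5)^5 = 1 − 0.975^5 = 0.119.

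**Simulation, 50 vs 50, chance that at least one of five non-mediators is flagged.**

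| Model | Measures | All five added | Only p<0.05 predictors added |
|---|---|---|---|
| Random intercept A | both types | 0.885-0.958 | not run |
| Random intercept B | not prognostic | 0.93-0.95 | 0.105-0.12 |
| Random intercept B | prognostic | 0.81-0.91 | 0.755-0.89 |
| Single time point | not prognostic | 0.91-0.95 | 0.06-0.09 |
| Single time point | prognostic | 0.70-0.95 | 0.19-0.85 |

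- A: 25 results per person, intercept SD 1.6-2.0, stratum log-odds difference 1.6, drug log-odds ratio 0 or 0.9, prognostic effect 0 or 0.6 per SD, independent measures, 400 trials per setting.
- B: 24 weekly results, intercept SD 2, stratum difference 2, drug log-odds ratio 0 or 1.0, prognostic effect 0 or 0.5 per SD, correlation 0 or 0.3, 600 trials per setting.
- Single time point: drug log-odds ratio 0, 0.6 or 1.0, prognostic effect 0, 0.2 or 0.4 per SD, correlation 0 or 0.3, 3,000 trials per setting.

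The value of 0.70 needs a large drug effect and correlated prognostic measures. Adjusting for a prognostic variable in a logistic model tends to push the treatment coefficient away from zero, so shrinkage is rarer there.

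**Measures relevant to Hypothesis 2.** In A, a single non-mediator fires in 42-47% of trials. For two independent measures: 1 − 0.58^2 = 0.66 to 1 − 0.53^2 = 0.72.

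**Would a threshold help?** Requiring at least 10% shrinkage, with all five added, gives 0.56-0.87 in A and 0.12-0.79 at a single time point. The result depends too much on the model to be a dependable repair.

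**Would later measures alone help?** In A, a genuine mediator (shifted 0.5 SD by treatment, 0.6 log-odds per SD) fires in 75% of trials and a prognostic non-mediator in 42%, a ratio of about 1.8. Moving to on-treatment measures while keeping the rule would still separate the two poorly.

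**The case against.** The strongest defence is that item 5 should not be reduced to its last sentence. Its first step looks at measure against outcome, item 4 looks at medication against measure for three of the five kinds, and the primary model looks at medication against outcome. With the shrinkage step, these are the familiar elements of a mediation argument. If items 4 and 5 were formally linked at 0.05, with independent measures and a 50% chance of shrinkage, the rate for item 4's three kinds would be about 1 − 0.975^3 = 7%, and at most 1 − 0.95^3 = 14%.

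Part of this stands. It would be wrong to infer that the plan never examines medication against these measures, or never examines the measures against outcome. But the plan does not join the pieces. Item 5 does not invoke item 4, and it says "we will add each of these measures to the models that assessed treatment effect" without limiting this to those that predict outcome. Even if the first step is a gate, the rate stays low only when no candidate is prognostic. Intake drug use severity plausibly is: Section 6 itself says that the presenting cocaine urine result predicts later use.

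It is also fair that a flagged demographic variable would not support Hypothesis 2, so the five-measure rate overstates the risk to that hypothesis. The rates for one or two measures are the relevant ones there.

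Finally, the plan's language is cautious: exploratory, preliminary, may mediate. No primary or secondary efficacy conclusion depends on item 5, and its wording presupposes a treatment effect to be explained. That limits the consequences, but does not make the rule informative.

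**Conclusion.** The point holds in limited form. As written, item 5 counts any reduction in the treatment coefficient, has no minimum change, test or interval, is not tied to item 4, and uses baseline measures that cannot mediate. It therefore says little about aim c, Hypothesis 2.

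The size depends on how item 5 is read, and the text does not settle that:

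- One variable per kind, all five added: roughly 80-97% of trials flag at least one non-mediator (as low as 70% in one single-time-point setting). Several variables per kind would raise this.
- One or two kinds relevant to Hypothesis 2, added without a gate: about 42-47% or 66-72%.
- Only p<0.05 predictors added: about 6-12% if none is prognostic, about 19-89% if they are.

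A reader might infer that the trial will announce a false mediator about nine times in ten. The documents do not support that as an unconditional statement: it assumes the first reading and near-independence, and the plan claims only preliminary evidence. The absence of an inferential criterion and the use of baseline measures do not depend on any simulated figure. The matter is worth correcting before analysis, but it does not threaten the efficacy results.

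**What to change.** Replace the last sentence of item 5 with a rule along these lines:

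- Take the non-drug reinforcement and activity measures at a named visit after randomisation, for example week 12, adjusted for the baseline value.
- Estimate (i) medication on the measure and (ii) the measure on abstinence after that visit, given medication and responder stratum.
- Report the indirect effect, on a stated scale, with a subject-level bootstrap confidence interval.
- Call it preliminary evidence of mediation only if the interval excludes zero at a level adjusted for the number of measures tested, for example Bonferroni-level intervals or Holm-ordered bootstrap p-values. List those measures in advance.
- Show the change in the treatment coefficient descriptively only, and say which coefficient is meant.
- Treat baseline measures as predictors or moderators, not mediators.

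No new data are needed: Section 4 already schedules these assessments at weeks 6, 12, 18, 24 and 30. The cost is SAP wording and a little more code. The intervals will be wide at N=100, and fewer measures will be flagged. The path from measure to abstinence is not randomised, so a positive result would still be preliminary.
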